2.4.4.3 Additional efficacy analysis(es)

2.4.4.3.1 Change from baseline analysis in other continuous endpoints

Change from baseline in FVC (% predicted and absolute) to Week 16-24 will be analyzed using the similar MMRM main statistical analysis model as for the key secondary endpoint, pre-BD FEV1, except that baseline FVC will replace baseline FEV1. Sex and baseline height will be excluded in the model for FVC % predicted as its value has been corrected for sex and height.

Changes from baseline in EXACT domain and total scores, EQ-5D-5L index score and VAS and SGRQ domain and total scores to Week 24 will be analyzed using the MMRM approach described for the analysis of the post-BD FEV1. The covariates will be treatment, baseline eosinophil strata, region, visit, treatment-by-visit interaction, baseline value and baseline-by-visit interaction. No imputation will be performed on missing values.

MMRM model including measurements up to Week 52 will also be used to derive LS mean change at all time points measured. Differences in LS means, the corresponding 95% CI, and the p-value will be provided for comparison of SAR440340 versus placebo, along with descriptive statistics. Similar analysis will be performed for the secondary efficacy population (high EOS group), without the baseline eosinophil strata in the model.

2.4.4.3.2 Analyses of the proportion of SGRQ responders

A logistic regression model will be used to compare percentage of SGRQ responder patients in SAR440340 and placebo at Week 24 (using the 4-point decrease from baseline as threshold). The model will include treatment, baseline eosinophil strata, region, baseline SGRQ total score value as covariates. Odds ratio of being a responder comparing SAR440340 to placebo will be provided along with the corresponding 95% CI and p-value. Descriptive statistics including number and percentage of responders will also be provided.

Similar analysis will be performed for the secondary efficacy population (high EOS group), without the baseline eosinophil strata in the model.

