- A common standard deviation of 0.3 L in each of the two groups is assumed, which is a consensus value based on the review of historical data from COPD trials.
- A difference of 0.12 L between the treatment group and the placebo group.
- A 2-sided t-test with 5% significance level.
- Fifteen percent (15%) of patients with missing data at Week 24 due to discontinuation or other reasons.
- Patients are randomized to the treatment group and the placebo group with a 1:1 ratio.

With these assumptions and 170 patients per group (340 patients in total), we will have 92.6% power to detect the difference of 0.12 L between the treatment group and the placebo group. The least significant difference between groups will be 0.07 L.

Randomization will be stratified by Screening/Visit 1 eosinophil count (see below) and by country.

To ensure scientific validity, alerts will be built into the interactive voice/web response system (IVRS/IWRS) to control the number of patients enrolled into each stratification groups, as follows:

1. Eosinophil <250 /mm³: approximately 50% (170) patients
2. Eosinophil ≥250 /mm³: approximately 50% (170) patients.

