1.5 MODIFICATIONS TO THE STATISTICAL SECTION OF THE PROTOCOL

A secondary efficacy population is added in the SAP. This secondary population includes all patients in the mITT population (the primary efficacy population) with baseline eosinophil values $\geq 250/\text{mm}^3$.

A tertiary endpoint, proportion of SGRQ responders at Week 24, is added. The SGRQ responders are patients whose Week-24 SGRQ total scores decrease 4 points or more from baseline. The corresponding efficacy analysis for this endpoint is logistic regression detailed in [Section 2.4.4.3.2](#).

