2.1.3.3.1 Patient-reported outcomes

COPD Assessment Test (CAT)

The CAT is a short, validated, patient-completed questionnaire to assess the impact of COPD on health status (see [Appendix C](#)). It comprises 8 questions that cover a broad range of effects of COPD on patients' health. Each question is scored in a range between 0 (I am very happy) and 5 (I am very sad), with the higher end indicating a higher impact of COPD on the patient's wellbeing. The CAT total score, the sum of the 8 individual question scores, ranges from 0 (best) to 40 (worst). This score is collected only at screening and baseline to assess patient eligibility.

St. George's respiratory questionnaire (SGRQ)

St. George's Respiratory Questionnaire (SGRQ) is a 50-item PRO instrument developed to measure the health status of patients with airway obstruction diseases (see [Appendix E](#)). The questionnaire is divided into two parts: part one consists of eight items pertaining to the severity of respiratory symptoms in the preceding 4 weeks; part two consists of 42 items related to the daily activity and psychosocial impacts of the individual's respiratory condition.

The SGRQ yields a total score and three domain scores (symptoms, activity, and impacts). The total score indicates the impact of disease on overall health status. This total score is expressed as a percentage of overall impairment; 100 represents the worst possible health status and 0 indicates the best possible health status (minimal clinically important difference: -4 units). Likewise, the domain scores range from 0-100, with greater scores indicative of greater impairment. See [Appendix F](#) for the scoring algorithm.

This questionnaire is assessed at baseline and at weeks 4, 8, 12, 24, 36, 52, 60 and 72.

Exacerbations of chronic obstructive pulmonary disease tool (EXACT)

The EXACT is a 14-item daily diary designed to provide a direct measure of patient-reported symptoms of COPD exacerbation (see [Appendix B](#)) and covers the following domains:

- Breathlessness (5 items),
- Cough and sputum (2 items),
- Chest symptoms (3 items),
- Difficulty bringing up sputum (1 item),
- Tired or weak (1 item),
- Sleep disturbance (1 item), and
- Scared or worried (1 item).

It is completed each evening before bedtime.

The EXACT total score is an interval-level scale ranging from 0 to 100, where higher scores indicate a more severe condition.

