2.5.3 Missing data

For categorical variables, patients with missing data are not included in calculations of percentages unless otherwise specified. When relevant, the number of patients with missing data is presented.

Handling of computation of treatment duration if investigational medicinal product end of treatment date is missing

For the calculation of the treatment duration, the date of the last dose of IMP is equal to the date of last administration reported on the end-of-treatment case report form page. If this date is missing, the exposure duration should be left as missing.

The last dose intake should be clearly identified in the case report form and should not be approximated by the last returned package date.

Handling of medication missing/partial dates

No imputation of medication start/end dates or times will be performed. If a medication date or time is missing or partially missing and it cannot be determined whether it was taken prior or concomitantly, it will be considered a prior and concomitant medication.

Handling of adverse events with missing or partial date/time of onset

Missing or partial adverse event onset dates and times will be imputed so that if the partial adverse event onset date/time information does not indicate that the adverse event started prior to treatment or after the treatment-emergent adverse event period, the adverse event will be classified as treatment-emergent. No imputation of adverse event end dates/times will be performed. These data imputations are for categorization purpose only and will not be used in listings. No imputation is planned for date/time of adverse event resolution.

Handling of adverse events when date and time of first investigational medicinal product administration is missing

When the date and time of the first IMP administration is missing, all adverse events that occurred on or after the day of randomization should be considered as treatment-emergent adverse events. The exposure duration should be kept as missing.

Handling of missing assessment of relationship of adverse events to investigational medicinal product

If the assessment of the relationship to IMP is missing, then the relationship to IMP has to be assumed and the adverse event considered as such in the frequency tables of possibly related adverse events, but no imputation should be done at the data level.

Handling of missing severity of adverse events

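### The tertiary Week 24 SGRQ responder analysis has no rule for a missing score, so by default it omits those patients and rests on a stronger missing-data assumption than the SGRQ mean-change model

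*SAP*

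**What the plan says.** The SAP adds the responder endpoint to those in the protocol. Section 1.5 defines it: "The SGRQ responders are patients whose Week-24 SGRQ total scores decrease 4 points or more from baseline". Section 2.1.3.3 lists it as tertiary.

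Section 2.4.4.3.2 sets the analysis: "A logistic regression model will be used to compare percentage of SGRQ responder patients in SAR440340 and placebo at Week 24". The covariates are treatment, baseline eosinophil stratum, region and baseline SGRQ total score. It names no handling of a missing Week 24 score and no sensitivity analysis. The nearest rule is in Section 2.5.3: "For categorical variables, patients with missing data are not included in calculations of percentages unless otherwise specified".

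Mean change is handled differently. In Section 2.4.4.3.1, "SGRQ domain and total scores to Week 24 will be analyzed using the MMRM approach described for the analysis of the post-BD FEV1", with visit, treatment-by-visit and baseline-by-visit terms, and "No imputation will be performed on missing values". On timing, Section 2.1.3.3.1 says "This questionnaire is assessed at baseline and at weeks 4, 8, 12, 24, 36, 52, 60 and 72".

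The planned multiple imputation (SAP 2.4.4.1, 2.4.4.2.1 and Appendix J) covers only the exacerbation rate and FEV1.

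**The concern.** A patient who gives SGRQ scores at Weeks 4 and 8 and then leaves contributes to the mean-change model but not to the responder comparison. The two analyses of one questionnaire then rest on different patients and different assumptions.

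- The mixed model is valid if missingness depends on observed data, including early SGRQ scores.
- The complete-case logistic model in general needs missingness to depend only on its own covariates: treatment, eosinophil stratum, region and baseline SGRQ.

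If patients leave because their early scores are poor, the first condition can hold while the second fails. The responder odds ratio can then be biased, and the two SGRQ results can disagree for a technical reason although the data that would help reconcile them are collected.

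**Working it through.** **1. The 15% planning value.** Protocol 9.2 assumes "Fifteen percent (15%) of patients with missing data at Week 24", stated for FEV1. To confirm that the plan's own power figure uses it, take n = 170 × 0.85 = 144.5 per arm, difference 0.12 L, SD 0.3 L, two-sided 5%:

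- Standard error = 0.3 × √(2/144.5) = 0.0353
- Power ≈ Φ(0.12/0.0353 − 1.96) = Φ(1.44) = 92.5%

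The protocol states 92.6%, so the figure reproduces. With no missing data (n = 170) it would be 95.8%. No power or missing-data figure is given for SGRQ. However, Protocol 9.2 and SAP 1.3 also assume cumulative study dropout of 9%, 15% and 20% by Weeks 12, 24 and 52. That is not specific to one endpoint, so 15% is a reasonable planning value here.

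**2. Patients left out.** 340 × 0.15 = 51 omitted and 289 analysed.

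**3. How many have early scores.** 340 × 0.09 = 30.6, so about 31 have left by Week 12. The remaining 51 − 31 = 20 or so leave between Weeks 12 and 24. Only those 20 would be expected to have all of Weeks 4, 8 and 12. The others may have Week 4 or 8, or no post-baseline score.

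**4. Illustration of sensitivity.** The documents give no responder rates and no dropout by arm, so everything here is assumed. Take 50% response on drug and 40% on placebo among patients with a score. The complete-case odds ratio is (0.5/0.5)/(0.4/0.6) = 1.50. For dropout fraction d:

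all-patient rate = (1 − d) × rate with a score + d × rate in dropouts

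Example with 20% dropout on drug, 10% on placebo and 20% response in dropouts: drug 0.8 × 0.5 + 0.2 × 0.2 = 0.44; placebo 0.9 × 0.4 + 0.1 × 0.2 = 0.38; odds ratio (0.44/0.56)/(0.38/0.62) = 1.28.

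| Dropout, drug/placebo | Complete-case | Dropouts respond at 20% | at 10% | at 0% (missing = non-responder) |
|---|---|---|---|---|
| 15%/15% | 1.50 | 1.42 | 1.43 | 1.43 |
| 20%/10% | 1.50 | 1.28 | 1.23 | 1.19 |
| 10%/20% | 1.50 | 1.58 | 1.65 | 1.74 |

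By a two-proportion z test, the complete-case p-value is 0.088 in every row. With missing counted as non-response it is 0.11, 0.45 and 0.014 in turn. With equal response among patients with a score (45% in each arm), counting missing as non-response under a 10-point imbalance moves the odds ratio from 1.00 to 0.83 (20%/10%) or 1.21 (10%/20%).

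**The case against.** Several stronger readings are tempting, and the documents do not support them.

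- **A reader might infer that the SAP expressly excludes these patients.** It does not. Section 2.5.3 speaks of percentages, not model inputs, and the definition in Section 1.5 could be read as counting a missing score as non-response. Complete-case is the likely default, inferred from that convention and the silence of Section 2.4.4.3.2. Two readings that give different odds ratios are themselves a reason to state the rule.
- **A reader might infer that only patients who stayed on treatment are compared.** Protocol 4.1 and 7.1.1 ask patients who stop treatment to continue visits, and a Week 24 score from such a patient counts.
- **A reader might infer that the odds ratio is overstated by 17 to 22%** (1.50 against 1.28 or 1.23). That needs more dropout on drug, which the documents do not predict; the opposite imbalance reverses the direction. Dropout that differs by arm does not by itself bias an odds ratio adjusted for treatment. Missingness must also relate to outcome given the covariates, and even then the odds ratio is preserved if the chance of being observed is a product of an outcome part and a covariate part.
- **A reader might infer that imputation would return the lower odds ratios in the table.** Imputation under missing-at-random uses treatment and observed scores. If early scores carried no information about dropout, it would return about 1.50.

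It is also fair that the SAP uses imputation for the key secondary endpoint only as a sensitivity analysis, that missing-as-non-responder is a simple and defensible alternative, and that much of the dropout occurs before Week 12, so imputation recovers only part of the lost information. These limit the weight of the point. They do not remove the unstated rule or the unused data.

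**Conclusion.** The point holds as a minor one. The responder analysis defaults to complete-case, would omit about 51 of 340 patients if SGRQ missingness matches the planned 15% study dropout, and rests on a stronger assumption than the SGRQ mixed model. Direction and size of any bias cannot be read from the documents; the odds ratios above show sensitivity under assumed rates and do not estimate the bias. With balanced 15% dropout the illustrated shift is small, from 1.50 to 1.42 or 1.43.

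The endpoint is tertiary, and SAP 2.4.4.4 makes all p-values nominal. The primary and key secondary conclusions are untouched and have their own missing-data sensitivity analyses. One caveat: the content of the SGRQ scoring appendix (SAP Appendix F) was not legible in the text available, so a rule for an absent questionnaire placed there would settle the default.

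**What to change.** In SAP 2.4.4.3.2, before unblinding:

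1. Multiply impute the missing Week 24 SGRQ total score from treatment, baseline score, the available Week 4, 8 and 12 scores and the other model covariates, with 40 imputations as already planned for FEV1.
2. Derive responder status in each completed data set, fit the stated logistic model and combine the log odds ratios by Rubin's rule. Do the same in the high-eosinophil population without the stratum term.
3. Report complete-case and missing-as-non-responder as sensitivity analyses, with the number of missing Week 24 scores by arm.

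The cost is one SAP paragraph and a little more programming, adapting the FEV1 imputation code in Appendix J. No new data are needed.

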2.4.4.3.3 Analyses of the other time-to-event endpoints

Time to the expanded AECOPD endpoint and time to first Clinically Important Deterioration (CID) up to week 52 will be analyzed using the same approach as the analysis of the time to first moderate or severe AECOPD. Similar analysis will be performed for the secondary efficacy population (high EOS group), without the baseline eosinophil strata in the model.

2.4.4.3.4 Analyses of actigraphy and home spirometry data (for patients in US and Canada only)

Change from the average of measurements over baseline and the average of measurements over Weeks 10-12 and over Weeks 22-24 in sleep parameters (total sleep time, wake after sleep onset, overnight activity counts) will be summarized (using mean, standard error, min, Q1, median, Q3 and max) in a table.

Similarly, change from the average of measurements over baseline and the average of measurements over Weeks 10-12 and over Weeks 22-24 in activity parameters (daytime activity counts, percent of time spent in sedentary activity, percent of time spent in moderate to vigorous physical activity) will be summarized (using mean, standard error, min, Q1, median, Q3 and max) in a table.

Change from the average of measurements over baseline and the average of measurements over Weeks 10-12 and over Weeks 22-24 in FEV1 (L) measured at home, will be summarized (using mean, standard error, min, Q1, median, Q3 and max) in a table, which will also include the summary of FEV1 (L) values from the in-clinic visits for the same group of patients.

Additional exploratory analyses may be conducted depending on data availability.

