
 To evaluate the clinical symptoms of COPD in patients treated with SAR440340 versus placebo 
 in all patients treated with SAR440340/placebo in subpopulations with high blood eosinophil level (≥ 250 /mm³) and low blood eosinophil level (<250 /mm³) in subpopulations according to use/no use of ICS with bronchodilators as background therapy, fibrinogen levels, and smoking status 	
 Time to first Clinically Important Deterioration (CID) as defined by decrease of >100 mL from baseline in trough FEV1 and /or deterioration in SGRQ by 4 units and/or moderate-to-severe AECOPD up to Week 24 (and over the 52 week variable treatment period)

 To evaluate the pharmacodynamics effects of SAR440340 	
 Blood eosinophil and neutrophil counts. Levels of biomarkers of the interleukin (IL)-33 and/or Type 2 inflammation pathway 
 Total IL-33, sST2 levels Calcitonin levels PARC levels Eotaxin-3 levels Total IgE levels Fibrinogen levels Induced sputum for RNA expression (optional for patients at a subset of sites). Optional: Messenger ribonucleic acid sequencing or whole transcriptome analysis. Optional: DNA/RNA sample will be collected for pharmacogenomic effects.

 Optional actigraphy (sleep and activity) and home spirometry (available for patients in US and Canada only): To evaluate the effects of SAR440340 compared to placebo on parameters of sleep, activity, and at-home spirometry. 	
 Change from average measurement over baseline (2 weeks prior to randomization) to average measurements over Weeks 10-12 (2 weeks prior to Visit 8) and Weeks 22-24 (2 weeks prior to Visit 14) of sleep and activity parameters. 
 Sleep: Total sleep time, wake after sleep onset, overnight activity counts Activity: Daytime activity counts, percent of time spent in sedentary activity, percent of time spent in moderate to vigorous physical activity Spirometry: FEV1

 Optional actigraphy (sleep and activity) and home spirometry (available for patients in US and Canada only): To compare the utility of at-home spirometry against in-clinic spirometry 	
 FEV1 (Spirometry performed at home) FEV1 (Spirometry performed at the clinic)

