8.1.1.5 Optional actigraphy and home spirometry assessments

Optional assessments of actigraphy (sleep and activity) and home spirometry will be available for patients in the US and Canada only. Patient will be issued an actigraphic wristband and asked to wear it continuously (including at night) throughout three monitoring periods defined in study flowchart ([Section 1.3](#)) on the nondominant hand, including at night. The actigraphic data is used to measure sleep parameters and daytime activity. The actigraph will be worn during the screening period as well as two monitoring periods during the treatment phase. Data from the device will be uploaded to a computer at each clinic visit following a monitoring period.

Patients will receive documented in-clinic training for use of ambulatory at-home spirometry during screening. During the study patients will be required to use at-home spirometry with electronic data storage to measure FEV1. Patients will be instructed to perform expiratory flow maneuvers as described in the study manual at least twice daily between 06:00 and 12:00 hour and between 18:00 and 24:00 hour during the screening period and for 2 week intervals during the treatment and follow-up period as indicated in the study flowchart.

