2.1.3.4 Exploratory efficacy endpoint(s)

- Change from the average of measurements over baseline to the average of measurements over Weeks 10-12 and over Weeks 22-24 in sleep parameters (total sleep time, wake after sleep onset, overnight activity counts), for patients in US and Canada only
- Change from the average of measurements over baseline to the average of measurements over Weeks 10-12 and over Weeks 22-24 in activity parameters (daytime activity counts, percent of time spent in sedentary activity, percent of time spent in moderate to vigorous physical activity), for patients in US and Canada only
- Change from the average of measurements over baseline to the average of measurements over Weeks 10-12 and over Weeks 22-24 in FEV1 measured at home, for patients in US and Canada only

The daily/nightly actigraphy (activity, sleep) and daily home spirometry data will be first averaged in the designated analysis windows and the resulted averages are used to calculate the change from baseline.

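### The table planned for the home-versus-clinic spirometry objective sets home FEV1 change beside clinic FEV1 values and specifies no within-patient difference, so as planned it cannot show agreement and does not clearly give the average bias

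*SAP*

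**What the plan says.** Protocol Section 3, Table 1, has two separate objectives for the optional home measurements. One concerns the effect of treatment on them. The other is "To compare the utility of at-home spirometry against in-clinic spirometry", with home FEV1 and clinic FEV1 listed as two endpoints and no paired quantity defined. Protocol Table 14 leaves exploratory analyses to the SAP.

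SAP 2.1.3.4 lists only the change from baseline "over Weeks 10-12 and over Weeks 22-24 in FEV1 measured at home", and says that daily home data are first averaged within the analysis windows. SAP 2.4.4.3.4 states that this change "will be summarized (using mean, standard error, min, Q1, median, Q3 and max) in a table". Clinic results enter only through a clause describing the contents of that output: "which will also include the summary of FEV1 (L) values from the in-clinic visits for the same group of patients". The section ends: "Additional exploratory analyses may be conducted depending on data availability". SAP 1.5, which records departures from the protocol's statistical section, does not drop the method-comparison objective.

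On test conditions, Protocol 8.1.1.5 asks for home manoeuvres "at least twice daily between 06:00 and 12:00 hour and between 18:00 and 24:00 hour" and refers to a study manual for how they are done. Protocol 8.1.1.2 requires bronchodilator washout before clinic pre-bronchodilator tests and prefers the morning.

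**The concern.** A comparison of two ways of measuring the same quantity in the same patient rests on the within-patient difference: its average (bias) and its spread (agreement). The planned table reports each method on its own, so the spread is not in it. It also describes the home measure as a change and the clinic measure as values, so the two columns are not on the same footing.

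Two further gaps make the columns hard to match. SAP Table 6 has windows for both pre- and post-bronchodilator clinic spirometry at Weeks 0, 12 and 24, and SAP 2.4.4.3.4 does not say which is meant. Nor does it say which visit is set against which home period.

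At stake is whether the twice-daily home tests asked of participating patients yield a report on this objective. If the agreement measure is chosen only after the data are seen, the choice is also open to the result.

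**Working it through.** The documents give no sample size, margin, agreement limit or SD of the home-clinic difference for this objective, so there is no figure to reproduce. The check is one of logic, with labelled assumptions for size.

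**1. Can the table give the average bias?** Let H and C be home and clinic FEV1, at baseline (0) and at a later time (t). The bias at t is mean(H_t − C_t). The table as worded gives mean(H_t − H_0) and mean(C_t). If home readings are off by a constant b throughout, then (H_t + b) − (H_0 + b) = H_t − H_0: the offset cancels, whatever its size. Adding the clinic baseline gives only the change in bias between the two times, mean(H_t − H_0) − [mean(C_t) − mean(C_0)]. The bias itself needs home levels, which SAP 2.4.4.3.4 does not commit to.

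**2. Can the table show agreement, even if both measures were printed as levels?** With equal SDs and within-patient correlation r:

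- SD of the difference = SD × √(2(1 − r))
- 95% limits of agreement = mean difference ± 1.96 × SD of the difference

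The marginal summaries fix the means and SDs but say nothing about r. With equal means, the half-width of the limits is:

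| r | SD 0.3 L | SD 0.5 L |
|---|---|---|
| 0 | ±0.83 L | ±1.39 L |
| 0.5 | ±0.59 L | ±0.98 L |
| 0.9 | ±0.26 L | ±0.44 L |
| 0.99 | ±0.08 L | ±0.14 L |

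The 0.3 L is borrowed from the FEV1-change power calculation in SAP 1.3, where it serves another purpose. The 0.5 L is an assumption. Every row of a column is compatible with the same planned table.

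**3. Same point without a formula.** Fifty simulated clinic values (normal, mean 1.3 L, SD 0.5 L) were copied as home values. Mean (1.282), SE (0.063), quartiles (1.050, 1.316, 1.561), minimum and maximum were identical. With each value paired to itself, r = 1.00 and the limits were ±0.00 L. With the same home values shuffled across patients, no listed statistic changed, but r = 0.13 and the limits were ±1.15 L. The draws are arbitrary (one fell just below zero), and real FEV1 pairs would not be near r = 0.13. The example shows only that the table cannot tell the two cases apart.

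**4. Size in a plausible range.** Assume a between-patient SD of 0.5 L, a difference SD of 0.2 to 0.3 L and 40 participants. The implied r is 1 − 0.2²/(2 × 0.5²) = 0.92 to 1 − 0.3²/(2 × 0.5²) = 0.82.

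- Limits of agreement: 1.96 × 0.2 = 0.39 L to 1.96 × 0.3 = 0.59 L
- 95% CI half-width for the mean difference, paired: 1.96 × 0.2/√40 = 0.06 L to 1.96 × 0.3/√40 = 0.09 L
- The same half-width if a reader builds it from two separate SEs: 1.96 × 0.5 × √(2/40) = 0.22 L

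**5. Is pairing feasible?** SAP 2.5.2 sets the averaging period at the 14 days before a visit. Applied to the target days in SAP Table 6, that is Days 71–84 for Week 12 (Day 85) and Days 155–168 for Week 24 (Day 169). The clinic pre-bronchodilator windows are Days 71–98 and 155–182. The pairs line up without new data.

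**The case against.** The strongest reply is that the plan delivers roughly what the protocol lists. The objective speaks of utility, not agreement. Its endpoints are two separate measures, and the SAP puts both in one table for the same patients. The closing sentence of SAP 2.4.4.3.4 leaves room for more, and for a descriptive objective with no test or decision rule a paired summary can be produced at any time. Much of this stands, and it limits the point in five ways.

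- A reader might infer that the objective cannot be answered. The documents do not support that: the paired data will exist, and only the analysis as planned falls short. The closing sentence, however, names no method and commits to nothing.
- A reader might equate utility with agreement. The protocol does not define the word, and it could cover completeness or variability. No analysis of those is specified either.
- A reader might say that the table can neither support nor refute agreement. That goes too far. Clearly different levels at matched times would count against agreement, and with complete pairs the difference of two means equals the mean paired difference. SAP 2.1.1 says generally that baseline efficacy values appear with on-treatment summaries, so home baseline levels may be shown. The bias is therefore not clearly obtainable, rather than ruled out.
- A reader might infer that home tests are done without withholding bronchodilators, or that morning and evening values are pooled. The first rests on silence, since Protocol 8.1.1.5 defers to a study manual not among these documents. On the second, SAP 2.1.3.4 does not say how the two daily readings are combined.
- The treatment effect on home FEV1 is a separate objective, and a correlation coefficient does not measure agreement. Neither is part of this point.

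**Conclusion.** The point holds in a limited form. SAP 2.4.4.3.4 commits only to marginal summaries, with home change beside clinic values and neither bronchodilator status nor matched visits stated. Such a table cannot show within-patient agreement, and it does not clearly give the average bias. That conclusion is logical and rests on no assumed number.

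The sizes do rest on assumptions: SDs of 0.3 or 0.5 L, correlations from 0 to 0.99, a difference SD of 0.2 to 0.3 L and 40 participants. Only the 0.3 L stands in the documents, and there it describes FEV1 change. The litre figures illustrate what the table would hide; they do not predict it.

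The consequence is small. The objective is exploratory and optional, for US and Canadian patients only, in a Phase 2a study that reports nominal p-values. This is a low-cost improvement to make before database lock.

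**What to change.** Add one paragraph to SAP 2.4.4.3.4:

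- For baseline, Week 12 and Week 24, compute each patient's home FEV1 (window average) minus clinic pre-bronchodilator FEV1 at the matching visit.
- Report the number of pairs, the mean difference with 95% CI and the 95% limits of agreement, with a Bland-Altman plot.
- Use morning home readings for the main comparison and the average of morning and evening readings as supportive.
- State the baseline home window. Protocol Table 1 gives two weeks before randomization; SAP Table 5 gives screening to Day -1.
- Note that the limits combine method error with day-to-day variation, because a multi-day average is set against a single clinic reading. They also include any difference in bronchodilator timing, which morning readings do not remove.

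The cost is one paragraph and one table or plot. No extra data, visits or patients are needed.
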